### 4.2 Controls and Minimization of Bias

All reasonable attempts will be made to control and minimize bias during this study, including the following:

- Consecutive enrollment of subjects will be employed to limit selection bias.

**Study Title:** Multi-site Anesthesia randomized controlled Study of End tidal control (Et Control) compared to conventional anesthesia Results (MASTER-Anesthesia Trial)  
**Study No:** 123.07-2015-GE5-0002

GE Healthcare

- Subjects will be randomized in a single-blind method to either the Et Control Arm or the Control Arm.
- Subjects will be blinded to their assignment; however, given the nature of the use of the investigational Et Control option during a case, the clinicians and Investigators cannot be blinded to the subject groups.
- Quotas or stratification criteria will be employed to ensure equitable distributions of patients and thus reduce spectrum bias.
- Multiple sites will be used to provide a broader cross-section of the population of patients and clinical practices, and thus reduce spectrum bias

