### 6.1.1 Investigational Et Control Arm

The subjects assigned to this group are induced and their airway secured based on each investigator's conventional intravenous induction and intubation practice. Machine log data are collected when the investigator initiates the start of anesthesia case on the Aisys CS.

The investigator will initiate Et Control after the airway is secured (intubation) and mechanical ventilation is initiated. Machine log data is collected when the investigator initiates the start of anesthesia case on the Aisys CS. Adjustments to the anesthesia machine settings, discontinuation of use of the investigational Et Control option, and changes to treatment are based upon clinician judgment for the wellbeing of the subject. This protocol does not in any way instruct the clinician to make any dosage changes or adjustments for study purposes. All dosage decisions are based on their normal clinical practice.

Aisys CS machine log data collection will end when an "end case" is confirmed on the Aisys CS at the end of the anesthesia case. Evaluable Aisys CS data ends when the patient is finally disconnected from the Aisys CS breathing system.

The clinician must continuously monitor measured inspired and end tidal oxygen and anesthetic concentrations to assess individual responses and compare to the target concentrations.

The clinician must maintain adequate ventilation to deliver appropriate oxygen and anesthetic agent to the patient. Et Control does not adjust ventilator parameters.

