### 8.1.7 Analysis of Adverse Events

Adverse events will be observed and recorded. Percent of subjects with AEs will be calculated, and comparisons between groups will be performed using Fisher exact test. Number of AEs and AE event rate will also be analyzed using non-parametric Wilcoxon method.

Analysis will be performed for a subset of adverse events of vital sign abnormalities including non-invasive blood pressure (NIBP), SpO2, and heart rate.

In addition, analysis of adverse events will be performed for each subset of patients defined by the pre-existing hypertension (*defined as a patient treated for hypertension*) status and ASA status.

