**Table 10-1 – Anticipated Adverse Events and Device Effects**

Event	Machine Failure	General Anesthesia	Aisys CS 	Et Control
Hypoxia	Insufficient oxygen delivery	x	x	x
	Incorrect oxygen concentration of fresh gas flow	x	x	x
	Insufficient ventilation	x	x	x
Hyperoxia	Excessive oxygen delivery	x	x	x
Cardiac Arrest	Incorrect anesthetic agent delivery	x	x	x
Intra-operative Awareness	Insufficient AA delivery	x	x	x
Hypertension	Insufficient anesthetic agent delivery	x	x	x
Hypotension	Excessive anesthetic agent delivery	x	x	x
Airway Fire	Electro-cautery in airway with high O 2	x	x	x

Adverse event assessment will be conducted from the time the subject provided consent to the end of the subject's participation in the study.

There is always a chance of unexpected risks. Throughout the study, the Sponsor will evaluate and update safety information in study documents.

**Study Title:** Multi-site Anesthesia randomized controlled Study of End tidal control (Et Control) compared to conventional anesthesia Results (MASTER-Anesthesia Trial)  
**Study No:** 123.07-2015-GE5-0002

GE Healthcare

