## 10.2 Adverse Event Definitions

**Adverse Event (AE):** As defined by EN ISO 14155-2011: any untoward medical occurrence, unintended disease or injury, or untoward clinical signs (including abnormal laboratory findings) in subjects, users or other persons, whether or not related to the investigational medical device.

**NOTE:** *This definition includes events related to the investigational medical device or the comparator. This definition includes events related to the procedures involved.*

Given the frequency at which physiological changes occur during the course of general anesthesia, the following definitions for changes in blood pressure, heart rate, and oxygenation will be used to determine adverse event reporting. If any of the parameters reach the below thresholds they shall be reported to the Sponsor as adverse events.

- (1) **Non-Invasive Blood pressure (NIBP):** defined as having the systolic blood pressure (SBP) reading < 70 mmHg or > 160 mmHg or mean arterial pressure (MAP) of < 55 mmHg or > 120 mmHg for > 5 minutes.
- (2) **Peripheral Capillary Oxygen Saturation (SpO2):** defined as having a value less than 90% for more than 5 minutes.
- (3) **Heart rate:** defined as the heart rate < 45bpm or > 110bpm for more than 5 minutes.

Additional adverse events related to physiological changes can be reported at the clinician's discretion.

**Serious Adverse Event (SAE):** As defined by EN ISO 14155-2011: an adverse event that

- a. led to death;
- b. led to a serious deterioration in the health of the subject, that either resulted in:
  - (1) a life-threatening illness or injury, or
  - (2) a permanent impairment of a body structure or a body function, or
  - (3) in-patient or prolonged hospitalization, or
  - (4) medical or surgical intervention to prevent life-threatening illness or injury or permanent impairment to body structure or a body function;
- c. led to fetal distress, fetal death, or a congenital abnormality or birth defect.

**NOTE:** *Planned hospitalization for a pre-existing condition, or a procedure required by the Clinical Investigation Plan (clinical protocol), without serious deterioration in health, is not considered a serious adverse event.*

**Anticipated Adverse Device Effect:** Any adverse event and/or reaction, the specificity or severity of which is consistent with the IRB approved informed consent, protocol, investigator brochure, or product labeling.

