## 15. MONITORING PLAN

### 15.1 Brief Description

In collaboration with the site, the Sponsor will ensure proper monitoring of the study to confirm that all the clinical requirements are met. There will be a minimum one monitoring visit made to each participating site after enrollment commences. Monitoring visits will ensure adherence to the protocol, completion of informed consents, IRB review of the study, maintenance of records, primary outcomes review and review of the eCRFs and source documentation for accuracy and completeness.

Other monitoring visits will be determined by GE Healthcare study team on an as needed basis. Remote data collection and monitoring may be completed on a pre-determined schedule.

During monitoring, the Sponsor will conduct 100% source data verification on all data collection on the eCRFs. Source data verification will not be completed on data collected electronically from the anesthesia machine or electronic medical records, including heart rate, blood pressure, SpO2, Et Control performance parameters (EtO2%, EtAA%), anesthesia machine settings (device log, anesthetic agent usage, user setting interactions), measured parameters, and alarms.

**Study Title:** Multi-site Anesthesia randomized controlled Study of End tidal control (Et Control) compared to conventional anesthesia Results (MASTER-Anesthesia Trial)  
**Study No:** 123.07-2015-GE5-0002

GE Healthcare

At the Close-out Visit, the monitor will collect all original documents contained in the site's Study Regulatory Binder. All study documents will be filed in the Clinical History File (CHF). Copies will remain in the binder at the site.

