### APPENDIX 3 – STUDY SCHEDULE OF PROCEDURES

STUDY ACTIVITY	SCREENING	RANDOMIZATION	INDUCTION AND INTUBATION PHASE	MAINTENANCE PHASE	EMERGENCE PHASE	PACU DISCHARGE	24 HR POST OPERATIVE 
	Data Collection						
Informed Consent 	•						
Inclusion/Exclusion Assessment	•						
Randomization		•					
Demographics	•						
Medical History	•						
Surgical History	•						
Concomitant Medications	•						
Current Surgery	•						
Physical Examination	•						
Laboratory Assessment ♦ pregnancy test, if applicable	•						
Height / Weight / BMI	•						
Heart Rate 	•		•	•	•	•	
Blood Pressure (systolic and diastolic) 	•		•	•	•	•	
Mean Arterial Pressure (MAP)	•		•	•	•	•	
SpO 2 	•		•	•	•	•	
Concomitant Medication (intravenous)			•	•	•	•	
Vasoactive Medication			•	•	•		
Inhalation Agent used prior to Intubation			•				
Time of Induction			•				
Time of Intubation			•				
Incision Time			•				
Et Control Initiation				• 			
Operative Positioning			•				
Airway Pressure			•	•	•		
Tidal Volume			•	•	•		

**Study Title:** Multi-site Anesthesia randomized controlled Study of End tidal control (Et Control) compared to conventional anesthesia Results (MASTER-Anesthesia Trial)

**Study No:** 123.07-2015-GE5-0002

GE Healthcare

STUDY ACTIVITY	SCREENING	RANDOMIZATION	INDUCTION AND INTUBATION PHASE	MAINTENANCE PHASE	EMERGENCY PHASE	PACU DISCHARGE	24 HR POST OPERATIVE 
	Data Collection						
EtO 2			•	•	•		
EtCO 2			•	•	•		
EtAA			•	•	•		
F i AA			•	•	•		
F i O 2			•	•	•		
Adverse Event Assessment 	•	•	•	•	•	•	•
End Time of Surgery					•		
Estimated Blood Loss					•		
Time subject is moved from the operating room					•		
Length of time in recovery room						•	
Time of admission to ICU or general ward						•	
Assess for intraoperative awareness							•
User Survey 					•		

1 Informed consent must occur prior to any screening activities.

2 Only applicable to investigational arm (Et Control).

3 These parameters will be collected from the electronic medical records (EMR).

4 There will be no follow-up visit after the 24-hour Post-Operative period.

5 Adverse Event Assessment will be performed from the time the subject provided consent to the end of study participation.

6 User survey to be completed after the emergence phase for each case.

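### Section 8.1.7 compares adverse events with no onset window, which dilutes the contrast between arms, and no stated step derives the vital-sign threshold events from the exported record or reconciles them with it

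*Combined protocol and SAP*

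**What the plan says.** **Collection window.** Section 10.1, below Table 10-1: "Adverse event assessment will be conducted from the time the subject provided consent to the end of the subject's participation in the study". A footnote to Appendix 3 agrees ("Adverse Event Assessment will be performed from the time the subject provided consent to the end of study participation"), and the schedule marks the assessment at screening and at randomization.

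**Analysis.** Section 8.1.7: "Percent of subjects with AEs will be calculated, and comparisons between groups will be performed using Fisher exact test", and "Number of AEs and AE event rate will also be analyzed using non-parametric Wilcoxon method". It adds an analysis of the adverse events that are vital-sign abnormalities, and subsets by hypertension and ASA status. None of these mentions onset. The safety population in section 8.1.2.1 limits which subjects are included, not which events.

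**When the arms part.** Section 6.1.1: "The investigator will initiate Et Control after the airway is secured (intubation) and mechanical ventilation is initiated". Under section 6.2.1 both groups receive standard care during induction and intubation.

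**Threshold events.** Section 10.2 sets numeric limits for blood pressure, SpO2 and heart rate, each lasting more than 5 minutes: "If any of the parameters reach the below thresholds they shall be reported to the Sponsor as adverse events". Further physiological events may be reported at the clinician's discretion. Section 4.2 says that "the clinicians and Investigators cannot be blinded to the subject groups".

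**The readings.** Section 6.3.2 takes heart rate, blood pressure, MAP and SpO2 from the electronic medical record (EMR), from induction through emergence. Readings are at least every 2.5 minutes in the first two hours and at least every 5 minutes afterwards. Section 14.3 sends the raw EMR data to the CRO. Section 15.1 requires full source verification of eCRF entries, but: "Source data verification will not be completed on data collected electronically from the anesthesia machine or electronic medical records, including heart rate, blood pressure".

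**The concern.** Two separate weaknesses affect the only listed safety endpoint (section 3.4.2).

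First, an event during induction or intubation arises before the device is in use. A subject who has one already counts as a subject with an adverse event, so any later event in that subject adds nothing to the Fisher comparison. The two percentages move closer together and a real difference becomes harder to see.

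Second, the vital-sign events are arithmetic rules on readings the sponsor's CRO will hold. Yet the events analysed in section 8.1.7 are those that reach an adverse-event form, completed by staff who know the arm. No stated analysis applies the rule to the readings or looks for crossings without a form. An event missed at that step also drops out of the section 8.1.9 summary of concentrations within 10 minutes of an event.

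The stake is how to read a finding of no difference. Section 3.1 says the trial is to support a US marketing application, and section 1.3.1 expects an equivalent risk profile. All nine feasibility adverse events were hypotension, six with Et Control (15 subjects) and three with control (13 subjects) (section 1.2.3), which is the kind of event these rules govern.

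**Working it through.** **1. Sample size.** The plan gives no size or power for the adverse-event comparison, so I take its 124 per arm. That figure reproduces from Table 8-1: non-inferiority t-test, margin 5, expected difference 90 − 87 = 3, SD 16, one-sided 0.025, power 0.95, giving 105 per arm; 105 / (1 − 0.15) = 124.

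**2. Dilution.** Let b be the share of subjects in each arm with an event before the arms differ, and p the rate of later events, taken as independent. Then

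- percent with any event = b + (1 − b)p
- difference between arms = (1 − b)(p_Et − p_con)

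The documents give no value for b or p. With assumed later rates of 15% v 30% (placed in either arm) and the planned Fisher exact test, two-sided 0.05, 124 per arm, exact unconditional power:

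| b | Rates compared | Difference (points) | Fisher power |
|---|---|---|---|
| 0% | 15.0% v 30.0% | 15.0 | 0.77 |
| 2% | 16.7% v 31.4% | 14.7 | 0.73 |
| 5% | 19.25% v 33.5% | 14.25 | 0.68 |
| 10% | 23.5% v 37.0% | 13.5 | 0.59 |
| 20% | 32.0% v 44.0% | 12.0 | 0.44 |
| 30% | 40.5% v 51.0% | 10.5 | 0.33 |

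A second scenario uses the feasibility counts as if each event were in a different subject, which the documents do not state: 6/15 = 40% v 3/13 = 23.1%. Power is 0.79 at b = 0 and 0.65, 0.52 and 0.41 at b = 10, 20 and 30%.

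**3. Uneven reporting.** Reported rate = capture fraction × true rate. The capture fractions are assumptions.

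- True rates 40% v 23.1%, control capturing all events and Et Control 90, 80 or 70%: the difference falls from 16.9 points to 12.9, 8.9 or 4.9, and Fisher power from 0.79 to 0.56, 0.30 or 0.11.
- No true difference, 30% in both arms, one arm capturing 80%: 24% v 30%, a spurious 6 points, significant in about 15% of trials.

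**4. Applying the duration rule.** Two consecutive readings 5 minutes apart span exactly 5 minutes, which is not more than 5; three span 10. At 2.5-minute spacing, three readings span 5 and four span 7.5. The same episode can therefore qualify or not depending on the interval and the counting rule. Section 6.3.2 also has the clinician return to the shorter interval when the subject is judged unstable. The plan gives no rule for this.

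**5. Limits in conflict.** The low systolic limit is < 70 mmHg in section 10.2 and < 75 mmHg in the glossary. For SpO2 below 90%, section 10.2 and one glossary entry require more than 5 minutes, while the glossary entry for hypoxia needs a single reading. Any derivation needs these reconciled first.

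**The case against.** Much can be said for the plan, and several stronger readings fail.

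- **Earlier events bias the comparison.** A reader might infer this, but they are balanced in expectation by randomization. They cost power and create no false signal. The factor (1 − b) applies only to the percent of subjects with any event. For event counts, also analysed in section 8.1.7, balanced earlier events leave the difference in means unchanged and add noise.
- **A hypertensive patient above the limits at screening would count as a threshold event.** Section 10.2 introduces the limits for changes in the course of general anesthesia and requires more than 5 minutes. Serial readings start at induction. The duration rule also removes brief excursions around intubation.
- **Sites choose which crossings to report.** Section 10.2 makes reporting mandatory; discretion covers only additional events. What remains is the risk of missed or uneven reports.
- **A missed crossing can never be found.** Section 15.1 has monitors review eCRFs and source documents for completeness. Its exclusion does not bar checking event forms against the EMR. The monitoring and data management plans are separate documents, not available here.

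The objection also limits the remedy. Replacing the all-event test with a windowed one would drop an event that began at induction and worsened under Et Control. Because clinicians know the arm and randomization precedes induction, care at induction could itself differ, and a windowed test alone would hide that. Both points stand, so the windowed comparison should be an addition.

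What the objection does not answer is that section 8.1.7 has no onset window and that no stated step links the readings to the event forms.

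**Conclusion.** The point holds as a cheap improvement to a secondary, unpowered comparison. That the comparison counts events from consent follows from section 8.1.7 setting no onset restriction; it is not stated outright.

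The loss depends on b, which is unknown. Under the assumed 15% v 30% it is slight at b = 2% (power 0.77 to 0.73) and large at b = 30% (to 0.33). Since screening and randomization fall within 24 hours before induction, most earlier events would probably arise during induction and intubation. The result rests on the assumed rates, independence of early and late events, and all 124 per arm contributing.

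The reporting half is a possible bias, not a demonstrated one. Its direction and size cannot be told from the documents.

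Collecting adverse events from consent is not an error, and nothing here touches the primary endpoints or the pass/fail criterion in section 8.4.

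**What to change.** In section 8.1.7:

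1. Keep the all-event comparison. Add a between-arm comparison of events with onset, or worsening, from the start of the maintenance phase as defined in section 6.2.2, a landmark that applies to both arms. Tabulate earlier events by arm.
2. Derive the blood-pressure, SpO2 and heart-rate events from the EMR readings, induction through emergence, with one program run without arm labels. Prespecify how the more-than-5-minutes rule applies to readings 2.5 or 5 minutes apart. Use the derived events for the vital-sign comparison alongside the site-reported ones, and query crossings that have no event form.
3. Before any derivation, reconcile section 10.2 with the glossary on the systolic limit and on SpO2 duration.

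Site reporting and safety reporting from consent stay as they are.

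Cost: SAP wording, one program and more data queries; the derived count may exceed the site-reported one. Onset time (section 10.3), machine-log data and EMR readings are already collected. Section 10.3 lists onset, resolution and severity but no time of worsening, so site-reported events that worsen need a stated convention.

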## 10.2 Adverse Event Definitions

**Adverse Event (AE):** As defined by EN ISO 14155-2011: any untoward medical occurrence, unintended disease or injury, or untoward clinical signs (including abnormal laboratory findings) in subjects, users or other persons, whether or not related to the investigational medical device.

**NOTE:** *This definition includes events related to the investigational medical device or the comparator. This definition includes events related to the procedures involved.*

Given the frequency at which physiological changes occur during the course of general anesthesia, the following definitions for changes in blood pressure, heart rate, and oxygenation will be used to determine adverse event reporting. If any of the parameters reach the below thresholds they shall be reported to the Sponsor as adverse events.

- (1) **Non-Invasive Blood pressure (NIBP):** defined as having the systolic blood pressure (SBP) reading < 70 mmHg or > 160 mmHg or mean arterial pressure (MAP) of < 55 mmHg or > 120 mmHg for > 5 minutes.
- (2) **Peripheral Capillary Oxygen Saturation (SpO2):** defined as having a value less than 90% for more than 5 minutes.
- (3) **Heart rate:** defined as the heart rate < 45bpm or > 110bpm for more than 5 minutes.

Additional adverse events related to physiological changes can be reported at the clinician's discretion.

**Serious Adverse Event (SAE):** As defined by EN ISO 14155-2011: an adverse event that

- a. led to death;
- b. led to a serious deterioration in the health of the subject, that either resulted in:
  - (1) a life-threatening illness or injury, or
  - (2) a permanent impairment of a body structure or a body function, or
  - (3) in-patient or prolonged hospitalization, or
  - (4) medical or surgical intervention to prevent life-threatening illness or injury or permanent impairment to body structure or a body function;
- c. led to fetal distress, fetal death, or a congenital abnormality or birth defect.

**NOTE:** *Planned hospitalization for a pre-existing condition, or a procedure required by the Clinical Investigation Plan (clinical protocol), without serious deterioration in health, is not considered a serious adverse event.*

**Anticipated Adverse Device Effect:** Any adverse event and/or reaction, the specificity or severity of which is consistent with the IRB approved informed consent, protocol, investigator brochure, or product labeling.

**Unanticipated adverse device effect (UADE):** As defined by 21 CFR 812.3: means any serious adverse effect on health or safety or any life-threatening problem or death caused by, or associated with, a device, if that effect, problem, or death was not previously identified in nature, severity, or degree of incidence in the investigational plan or application (including a

**Study Title:** Multi-site Anesthesia randomized controlled Study of End tidal control (Et Control) compared to conventional anesthesia Results (MASTER-Anesthesia Trial)  
**Study No:** 123.07-2015-GE5-0002

GE Healthcare

supplementary plan or application), or any other unanticipated serious problem associated with a device that relates to the rights, safety, or welfare of subjects.

**Adverse Device Effect (ADE):** An adverse event related to the use of an investigational medical device [ISO 14155:2011 3.1]. This includes any adverse events resulting from insufficient or inadequate instructions for use, deployment, implantation, installation, or operation, or any malfunction of the investigational medical device. This includes any event that is a result of a user error or intentional misuse of the investigational device [ISO 14155:2011 3.43].

**Serious Adverse Device Effect (SADE):** An adverse device effect that has resulted in any of the consequences characteristic of a serious adverse event [ISO 14155:2011 3.36].

**Device deficiency:** An inadequacy of a medical device with respect to its identity, quality, durability, reliability, safety, or performance, such as malfunctions, use errors, and inadequate labelling [ISO 14155:2011 3.15].

**Unanticipated serious adverse device effect (USADE):** A serious adverse device effect, which by its nature, incidence, severity, or outcome has not been identified in the current version of the risk analysis report [ISO 14155:2011 3.42]. In the United States, any serious adverse effect on health or safety or any life-threatening problem or death caused by, or associated with, a device, if that effect, problem, or death was not previously identified in nature, severity, or degree of incidence in the study documents, will be reported in accordance with 21 CFR 812.3 and applicable laws and regulations.

